Timing of Assessments: Initial evaluations will be performed \leq 14 days before starting natural progesterone. Subsequent evaluations will be at the following time points after initiation of study therapy (4 weeks \pm 3 days, 8 weeks \pm 1 week, 24 weeks \pm 2 weeks) with one final off-study evaluation if it is prior to the 24 week evaluation and $>$ 2 weeks from previous evaluation (this evaluation would be the visit when patient comes off study).

QOL Questionnaires: EORTC Quality of Life Questionnaire-Core 30/Brain Cancer Module-20 (EORTCQLQ30/BN20); M. D. Anderson Symptom Inventory Brain Tumor Module (MDASI-BT)

2. Objectives (and Endpoints)

Our main goal is to establish pharmacokinetics, safety/tolerability and efficacy of daily subcutaneous natural progesterone for the treatment of patients with recurrent glioblastoma. The specific objectives/endpoints of this study are listed below.

OBJECTIVES	ENDPOINTS
Primary	

Protocol Title: Pilot study of progesterone for recurrent GBM

OBJECTIVES	ENDPOINTS

To determine that the pharmacokinetics of natural progesterone given to recurrent GBM patients by subcutaneous injection is consistent with previous determinations made using the aqueous formulation of progesterone (IBSA Institut Biochimique SA, Lugano, Switzerland) given subcutaneously.To determine the safety of administering daily subcutaneous natural progesterone for the treatment of patients with recurrent GBMs.To determine the ORR [defined as stable disease (SD) or better (PR or CR)] at 8 weeks in eligible patients with recurrent GBM treated with daily subcutaneous natural progesterone.	
Pharmacokinetic: Plasma progesterone levels at 0, 30 min, 1, 2, 4, 6, 8 hrs from 1st injection and at 8 prior to drug injection in 3 pts at each dose level. (May alternatively be done on any day after the 1st week during the initial 4 weeks with no need for day 8 trough draw if done later)Safety: Adverse events, clinical assessments (eg. vital sign, physical, etc.), clinical laboratory test.Efficacy: Overall response rate (ORR) per protocol volumetric definition at 8 weeks from initiation of progesterone.
Secondary	

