 - Age \geq 55 years and one year or more of amenorrhea
 - Age $<$ 55 years and one year or more of amenorrhea, with estradiol $<$ 20 pg/ml
 - Age $<$ 55 with prior hysterectomy but intact ovaries, with estradiol $<$ 20 pg/ml
 - Prior bilateral oophorectomy

Toxicity (Adverse Event) assessment

Toxicities will be scored according to CTCAE v5.0. Evaluations for toxicity will be performed weekly during the 1st 4 weeks of progesterone therapy followed by every 4 weeks thereafter (through a total of up to 24 weeks drug therapy). Final assessment (EOS visit) will be 4 weeks after last drug dose.

MRI brain with and without contrast

Diagnostic brain MRI scans with and without contrast will be utilized to assess for response with timing according to the Schedules of Assessments. DSC perfusion imaging will also be obtained, if possible, but is not required. Volumetric assessment of progressive measurable contrast-enhancing disease ($\geq 1 \text{ cm}^3$) will be performed at baseline. If there is no measurable disease at trial baseline scan (e.g. gross resection of all recurrent enhancing disease), patient is still eligible for study but will be assessed for progression based on criteria for non-evaluable disease ($< 1 \text{ cm}^3$ of recurrent enhancing disease).

Imaging response criteria is defined below:

Measurable Disease: Measurable lesions are those with clearly defined margins by contrast-enhanced MRI scan that is at least 1 cm^3 in volume. All measurable lesions will be considered together. Clear enhancing lesions representing progressive tumor pre-treatment that is less than 1 cm^3 in volume will be considered non-evaluable disease.

Objective Status, To Be Recorded at Each Evaluation: Unless progression is observed, objective status can only be determined when ALL measurable sites and lesions are assessed.

Response Definitions:

- **Complete Response (CR):** Complete disappearance of all measurable disease in contrast-enhancing MRI. No new lesions. No evidence of non-evaluable disease. All measurable lesions and sites must be assessed using the same techniques as baseline. Patients must be on no steroids. If there is no enhancing disease present at baseline, then this criteria will not apply and the case will not be considered in the N when evaluating for % of patient achieving CR.

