- **Partial Response (PR):** (Measurable disease only) Greater than or equal to 65% decrease under baseline in total tumor volume of all measurable lesions. No progression of non-evaluable disease (defined as progression to at least 1.5 cm^3 in volume). No new lesions. All measurable lesions and sites must be assessed using the same techniques as baseline. If there is only non-evaluable disease or no enhancing disease present at baseline, then this criteria will not apply and the case will not be considered in the N when evaluating for % of patient achieving PR.
- **Stable Disease (SD):** Does not qualify for CR, PR, or progression. The designation of SD requires a minimum of 8 weeks duration (2 assessment of stable disease from baseline at least 4 weeks apart). All measurable sites must be assessed using the same techniques as baseline. The steroid dose at the time of the scan evaluation should be no greater than the maximum dose used in the first 8 weeks from initiation of therapy.
- **Progressive Disease (PD):** 40% increase in the tumor volume of all measurable lesions over previous exam (over baseline if no decrease) using the same techniques as baseline, OR clear progression of non-evaluable disease (defined as growth to at least 1.5 cm^3 in volume), OR clear appearance of any new measurable lesion/site, OR clear clinical worsening or failure to return for evaluation due to death or deteriorating condition (unless clearly unrelated to this cancer).

Best Response: This will be calculated from the sequence of objective statuses. For patients with all disease sites assessed every evaluation period, the best response will be defined as the best objective status as measured according to the above criteria.

Pharmacokinetic Testing (Research)

Protocol Title: Pilot study of progesterone for recurrent GBM

Number of patients tested: The first three patients of a treatment dose level will be undergo pharmacokinetic testing for plasma level of progesterone.

Timing of Assessments: Pharmacokinetic samples will be obtained on day 1 of therapy. Plasma samples will

be obtained immediately prior to administration of drug and, subsequently, at 30 minutes, 1 hour, 2 hour, 4 hours, 6 hours, and 8 hours after drug injection. Additional sample will be obtained prior to the day 8 injection. (May alternatively be done on any day after the 1st week during the initial 4 weeks with no need for day 8 trough draw if done later)

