- Patients who received any other in anti-tumor agents (including investigational anti tumor agents, but excluding avastin) must be off therapy for 4 weeks prior to initiating progesterone on study. Patients on avastin at enrollment will be allowed to be maintained on their current dose of avastin when they begin progesterone. Patients receiving anti-coagulation therapy are excluded.
- Patients that underwent resection for their recurrent GBM need to wait at least 4 weeks before they can initiate progesterone treatment.
- Patients with active or recent (within 6 months) thromboembolic disease are excluded.
- Patients with current ongoing therapy with estrogen/progesterone (including hormonal contraceptives) are excluded. Would need to stop this form of birth control at least 7 days prior to initiation of therapy to be eligible.

10. Local Number of Participants

We will be recruiting all participants (up to 32 patients) at the Winship Cancer Institute of Emory University. Patients will be registered after signing of the informed consent document and meeting all entry requirements.

11. Recruitment Methods

Subjects will be recruited from recurrent GBM patients referred by neurosurgery, neuro-oncology or radiation oncology. Initial screening will be conducted/reviewed by clinical investigators and/or their trained designee (e.g. research nurse, research coordinator, etc.). Cases will be identified from the neurosurgery/neuro-oncology/radiation oncology outpatient clinics or neurosurgery/oncology inpatient services. After potential subjects have been identified, their clinical care team at Winship will inform potential subjects about the known benefits and potential risks of a clinical trial as well as other available treatment options.

Protocol Title: Pilot study of progesterone for recurrent GBM

Some of the subjects recruited for this protocol will be patients being treated at Emory and under the care of one or more of the study investigators. Some potential subjects will be identified by their treating physician and referred to Emory for possible participation in the protocol.

No incentives are provided to patients for trial participation.

Study personnel will notify Winship Central Subject Registration (WCSR) by email at [contact], once subject has been consented for a trial.

Email notification must be done within 24 hours after consent has been obtained and it will include scanned copies of:

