Futility analysis - As mentioned above, there will be one interim analysis for futility. It is known that random ineffective therapies for recurrent GBM may still produce a response rate of 10%. Therefore, the overall response rate (ORR) for first 10 patients (1/2 of planned expansion cohort size) that undergo treatment with the subcutaneous progesterone at the final dose from the dose finding phase of the study will be determined. If the ORR at the 8 week assessment time point is 20% (2 of 10) or greater, then the study will be declared potentially non-futile and enrollment of the full expansion cohort (N=20) will proceed. If the ORR at this time point is 10% (1 of 10) or less, then the study will be declared futile and further enrollment will be aborted. If the study is declared futile at this interim analysis, new enrollment will be discontinued but any patients that is still on therapy at that time will be allowed to continue therapy as long as they meet criteria to continue therapy as defined in Section 8.1 (e.g. continue to not have protocol-specified progressive disease).

Analysis populations:

Safety population: All subjects enrolled in the study who received the study drug.

Efficacy population: Subjects enrolled in the study who received the study drug at the expansion dose from both the dose finding and expansion phases of study.

Data analysis plan for each objective is listed below:

Primary Objectives

Dose finding phase (Part 1):

- To determine the safety of administering daily subcutaneous natural progesterone for the treatment of patients with recurrent GBMs. The safety of this approach will be confirmed by assessing toxicity potentially attributable to the daily progesterone treatment. Toxicity will be determined by CTCAE v5.0 criteria. The MTD will be determined using the standard 3+3 approach. **Dose escalations will be reviewed by the Winship Data Safety Monitoring Committee (DSMC) (per Winship SOP 7.9 Dose Escalation Determinations for Sponsor-Investigator or Investigator Initiated Studies).** **The PI or designee will provide an update on all relevant safety data of patients entered to a dose level to the DSMC when dose escalation is planned. Upon obtaining approval from the DSMC, dose escalation can proceed.**

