- To determine the pharmacokinetics of natural progesterone given to recurrent GBM patients by subcutaneous injection. This analysis will be performed to determine what plasma drug levels can be achieved in recurrent GBM patients with subcutaneous administration of natural progesterone and whether this is in line with what was previously determined in healthy subjects.

Dose expansion phase (Part 2):

- To determine the overall response rate (ORR) of eligible patients with recurrent GBM treated with daily subcutaneous natural progesterone. This primary analysis will be performed on all patients treated at the expansion dose (from either the dose finding or expansion phases). In particular, we will be looking for the fraction of patients that are able to maintain at least stable disease (SD), given our expectation that, for patients showing a contrast enhancing recurrence, all will continue to progress unless they are receiving an effective therapy. ORR will be reported, and an exact 95% confidence interval will be reported using the Clopper-Pearson method. There will be one interim analysis for futility that is described above that may halt enrollment before full accrual of the expansion cohort.

Secondary Objectives

Dose expansion phase (Part 2):

- To determine and compare the progression free survival of eligible patients with recurrent GBM. Patients on this study will be followed for progression free survival (PFS), which is defined from the time of pre-treatment MRI to the time of either radiographic progression or death, whichever occurs first. Both actuarial PFS curves and 24-week PFS (for expansion dose patients and all patients as separate analyses) will be estimated using the Kaplan-Meier method, and compared to matched historical controls using log-rank tests and univariate Cox proportional hazards models. The matched effects will be estimated by a Cox model with a robust variance estimator. A 95% confidence interval will be provided for 24-week PFS using the Greenwood formula to estimate the standard error.

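### The primary 8-week rate and the futility count include resected and avastin-treated patients, in whom stable disease is weak evidence that progesterone works

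*Combined protocol and SAP*

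**What the plan says.** Section 2 states the primary efficacy objective: "To determine the ORR [defined as stable disease (SD) or better (PR or CR)] at 8 weeks". Section 15.1 defines the efficacy population as "Subjects enrolled in the study who received the study drug at the expansion dose from both the dose finding and expansion phases of study", and says of the ORR: "This primary analysis will be performed on all patients treated at the expansion dose (from either the dose finding or expansion phases"). Neither definition mentions measurable disease or concurrent treatment. The reason given for treating SD as a signal is narrower: "for patients showing a contrast enhancing recurrence, all will continue to progress unless they are receiving an effective therapy".

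The futility rule (Sections 5.2 and 15.1) counts the first 10 patients at the final dose. Enrollment continues with 2 or more successes and stops with 1 or none. The benchmark is: "It is known that random ineffective therapies for recurrent GBM may still produce a response rate of 10" percent.

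Three other provisions decide who is in these counts and how they are scored:

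- **Resected patients.** Section 5.7: "If there is no measurable disease at trial baseline scan (e.g. gross resection of all recurrent enhancing disease), patient is still eligible for study". The synopsis and the inclusion criteria in Section 9 agree. The screening list in Section 5.6, however, asks for an MRI showing at least 1 cm³ of progressing enhancing tumor and makes no exception.
- **Response definitions (Section 5.7).** For the percentage with PR, a patient with only non-evaluable or no enhancing disease at baseline is set aside: "the case will not be considered in the N when evaluating for % of patient achieving PR". A similar exclusion for CR covers only patients with no enhancing disease. SD has no such exclusion.
- **Avastin.** The exclusion criteria in Section 9 allow it to continue: "Patients on avastin at enrollment will be allowed to be maintained on their current dose of avastin when they begin progesterone". No cap, stratum or separate analysis is planned.

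**The concern.** The argument for reading SD as activity does not cover everyone in the analysis set. A patient whose recurrence has been resected may show no progression at 8 weeks because of the surgery. A patient continuing avastin may be stable because of avastin, which the protocol itself lists as an exception among anti-tumor agents. Both count as successes on the same footing as a patient with a measurable, growing tumor and no other treatment.

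The primary rate would then depend partly on how many such patients happen to enroll, which the plan neither limits nor predicts. The futility rule could also declare an inactive drug potentially non-futile through case mix alone.

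**Working it through.** The plan states no alpha, power, target rate or error rate for N = 20 or for the futility rule, so there is no design figure to reproduce. Its cut-offs are consistent (2/10 = 20%, 1/10 = 10%).

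**1. Imaging thresholds for progression (Section 5.7).** Measurable disease progresses at a 40% volume increase, that is 1.4-fold. Disease under 1 cm³ must reach 1.5 cm³, that is 1.5/baseline-fold. Assuming exponential growth over 56 days, the longest doubling time that reaches a given fold increase is 56 × ln 2 / ln(fold).

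| Baseline disease | Fold needed | Progression by 8 weeks if doubling time is at most |
|---|---|---|
| 1.0 cm³, measurable | 1.4 | about 115 days |
| 0.5 cm³ residual | 3.0 | about 35 days |
| 0.2 cm³ residual | 7.5 | about 19 days |

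By imaging alone, a 0.2 cm³ residual with a doubling time between about 19 and 115 days does not progress, while a measurable tumor growing at the same rate does.

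**2. Futility rule with the benchmark applied to everyone.** P(X ≥ 2 | n = 10, p = 0.10) = 1 − 0.9¹⁰ − 10 × 0.1 × 0.9⁹ = 1 − 0.349 − 0.387 = 0.264.

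**3. Futility rule with a mixed first ten, inactive drug.** Let k of the ten be resected, each with SD probability q, and let the other 10 − k have success probability 0.10. The pass probability is P(A + B ≥ 2), with A ~ Binomial(10 − k, 0.10) and B ~ Binomial(k, q). Neither k nor q is in the documents; both are assumptions shown as a range.

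For k = 3, q = 0.5:
- P(0) = 0.9⁷ × 0.5³ = 0.4783 × 0.125 = 0.060
- P(1) = 7 × 0.1 × 0.9⁶ × 0.125 + 0.9⁷ × 3 × 0.125 = 0.0465 + 0.1794 = 0.226
- Pass = 1 − 0.060 − 0.226 = 0.714

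| Resected among first 10 | q = 0.3 | q = 0.5 | q = 0.7 |
|---|---|---|---|
| 0 | 0.264 | 0.264 | 0.264 |
| 1 | 0.341 | 0.419 | 0.496 |
| 2 | 0.421 | 0.581 | 0.746 |
| 3 | 0.497 | 0.714 | 0.887 |
| 5 | 0.633 | 0.879 | 0.981 |

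Section 15.1 expects every enhancing recurrence to progress without effective therapy. Setting 0.10 to 0 to match, three resected patients alone pass the rule with probability 0.216, 0.500 or 0.784 at q = 0.3, 0.5 or 0.7.

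**4. Final estimate, N = 20.** The smallest count whose exact 95% interval excludes 10% is 6/20 (11.9% to 54.3%). An inactive drug reaches it with probability 0.011 if all patients have a 10% rate. If 6 of 20 are resected, the probability is 0.080, 0.246 or 0.518 at q = 0.3, 0.5 or 0.7. The plan specifies no test; this shows only how the reported interval could mislead.

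**5. Avastin.** The documents give no rate of 8-week SD on avastin alone, so no calculation is possible. Only the direction can be stated: if avastin itself holds disease stable, the rate attributed to progesterone is too high.

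**The case against.** Several points on the other side are sound.

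- **SD is not automatic.** A reader might infer that a resected patient is stable by default. Section 5.7 does not support that: clinical worsening, or failure to return because of death or deterioration, is progression, and so is a new measurable lesion. SD also needs two assessments at least 4 weeks apart and carries a steroid-dose condition. These lower q, but they do not close the gap in the imaging threshold.
- **ORR has one denominator.** The exclusions for CR and PR could suggest that the parts of ORR are computed on different patients. They apply only to the separate CR and PR percentages; ORR is a single proportion over the efficacy population. What remains is that the plan recognizes these patients cannot show such responses, yet counts their SD without comment.
- **The 10% is for recurrent GBM generally.** It is not stated to be a rate for measurable disease. If it already averages over a similar case mix, the pass probability stays near 0.26. The plan does not say so.
- **Avastin continues for a reason.** Section 5.5 cites rebound and interpretability. That addresses the effect of stopping avastin, not what SD means while it continues. If Section 5.6's requirement for progressing tumor applied to these patients, the confounding would be weaker, but the inclusion criterion in Section 9 does not require progression on avastin.
- **This is a pilot.** Part 2 gives a preliminary estimate without a test, and PK and safety are unaffected. But the rate is a primary endpoint, and the futility rule decides whether enrollment continues.

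Appendix 4 expands ORR as objective response rate, but Section 2 defines it openly as SD or better, so the label is cosmetic.

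**Conclusion.** The concern holds in this form: the primary rate and the futility count include patients to whom the plan's own argument for SD does not apply, and those without measurable disease face a looser imaging threshold for progression. SD is likelier in them, not certain.

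The size rests on three assumptions: that the 10% applies to measurable, avastin-free patients, the resected share, and their SD rate on an inactive drug. On those terms the chance of passing futility rises from 0.26 to 0.34–0.50 with one resected patient in ten, 0.50–0.89 with three and 0.63–0.98 with five. The upward direction needs only that these patients' SD rate exceeds 10%.

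A reader might go further and conclude that the rule can no longer stop an inactive drug. The figures do not support that: with three of ten resected it still stops 11% to 50% of the time, against 74% with none. Nor can any number be put on avastin. If Section 5.6 were applied literally, non-measurable patients would not enroll and that part would fall away, but three other places in the protocol admit them.

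**What to change.** In Section 15.1:

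1. Define the primary SD-or-better rate on expansion-dose patients with at least 1 cm³ of measurable enhancing disease at baseline. Report it separately by measurable disease and by avastin use, with exact intervals. Keep all expansion-dose patients as a supportive analysis, and report CR + PR separately.
2. Apply the 2-of-10 rule to the first 10 patients with measurable disease. If that delays the look too far, keep the first 10 treated, show the count by measurability and avastin use, and do not declare non-futility on SD in non-measurable patients alone.
3. Reconcile the screening requirement in Section 5.6 with the synopsis, Section 5.7 and Section 9.

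Eligibility and treatment need not change for items 1 and 2. Avastin patients with measurable disease stay in the primary set, so separate reporting makes that confounding visible but does not remove it.

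The cost is precision and time. If 14 of 20 have measurable disease, 3/14 has an exact 95% interval of 4.7% to 50.8%, against 5.7% to 43.7% for 4/20. Ten measurable patients require about 14 enrolled if 30% are resected (10/0.7), some 2 to 4 months later at the planned 1–2 patients per month. At 50% resected it takes about 20 (10/0.5), which is full accrual, so the look would save nothing; hence the alternative in item 2.

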- Brief medical history, symptom-directed physical exam including KPS and neurologic assessment (on day 15, on day 29, every 4 weeks thereafter). Can be performed at ± 3 days during first 8 weeks and ± 7 days thereafter.
- Vitals signs, weight (on day 15, on day 29, every 4 weeks thereafter). Can be performed at ± 3 days during first 8 weeks and ± 7 days thereafter.
- Review of concomitant medications (including steroid and anti-seizure med documentation, every week during 1st 4 weeks, every 4 weeks thereafter). Can be performed at ± 3 days during first 8 weeks and ± 7 days thereafter.
- Drug diary documentation by patient (to be collected every two weeks when patient return to get new supply of medication).
- MRI brain w/ and w/o contrast (after 4 weeks, after 8 weeks, every 8 weeks thereafter). Can be performed at ± 1 week at the after 4 weeks MRI and ± 2 weeks thereafter.
- Adverse event (AE) assessment (every week during 1st 4 weeks, every 4 weeks thereafter). Can be performed at ± 3 days during first 8 weeks and ± 7 days thereafter.
- QOL assessment after 4 weeks ± 3 days, after 8 weeks ± 1 week, after 24 week ± 2 weeks (assess for final time if patient comes off study before 24 weeks and it is > 2 weeks from previous assessment).
- Serum sample for exploratory biomarkers after 4 weeks ± 3 days.
- Pharmacokinetic assessment on day 1 (0, 30 minutes, 1, 2, 4, 6, 8 hrs from drug injection) as well as at day 8 prior to drug injections (only in first 3 patients at each dose level). (May alternatively be done on any day after the 1st week during the initial 4 weeks with no need for day 8 trough draw if done later)
- Clinical laboratory tests for:
 - CBC with differential
 - CMP

Post-Treatment Phase

The **Post-Treatment Phase** is the period after progesterone is stopped to the end-of-study (EOS) visit. The EOS visit will be scheduled 28 days after discontinuation of progesterone (window for visit can be up to 2 weeks beyond 28 days).

The following will be performed at the EOS visit:

- Brief medical history, physical exam including KPS and neurologic assessment.
- Vitals signs, weight.
- Review of concomitant medications (including steroid and anti-seizure med documentation).
- AE assessment.
- Clinical laboratory tests for CBC with differential and CMP.

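### The 8-week response rate is given a fixed-sample exact interval although enrollment can stop at 10 patients; the effect is small except at 2 to 4 of 20

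*Combined protocol and SAP*

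**What the plan says.** Sections 5.2 and 15.1 of the combined protocol and SAP set one futility look at the first 10 patients treated at the expansion dose. With two or more successes, "the study will be declared potentially non-futile and enrollment of the full expansion cohort (N=20) will proceed". With one or none, "then the study will be declared futile and further enrollment will be aborted". The wording is binding. Success means stable disease or better at 8 weeks (Section 2).

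The efficacy population is everyone treated at the expansion dose, so the interim patients also count in the final analysis. For that analysis Section 15.1 states: "ORR will be reported, and an exact 95% confidence interval will be reported using the Clopper-Pearson method". The next sentence reads: "There will be one interim analysis for futility that is described above that may halt enrollment before full accrual of the expansion cohort". The look is therefore acknowledged, but nothing says that it changes the estimate or the interval.

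Section 15.1 gives no target rate, power or type I error for the expansion. Its only benchmark is 10% for ineffective therapy. No section says whether accrual is held while the tenth patient reaches week 8.

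**The concern.** Clopper-Pearson limits come from binomial tail probabilities at a fixed n. Here a total of 2, 3 or 4 out of 20 can arise only if at least two of the first ten succeeded, and trials with a poor first stage never reach 20. The sampling distribution is not Binomial(20, p), so the exact label no longer carries its guarantee.

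The expansion is described as a preliminary efficacy assessment, so the estimate and its interval are its main product. An upper limit that is too low could lead a reader to rule out activity that the design has not excluded.

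The same silence affects conduct. If enrollment continues during the 8-week wait, patients start treatment before a possible futile call, and the plan has no explicit rule for handling them in the analysis.

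**Working it through.** **Inputs.** First stage n1 = 10, stop at 1 or fewer, total N = 20 (Sections 5.2 and 15.1). Interval method: Clopper-Pearson, 95% (Section 15.1). Accrual: 1 to 2 patients per month (Section 9). Endpoint at 8 weeks. The plan has no power or error rate to reproduce; its simple figures agree (10 is half of 20, 2/10 = 20%, 1/10 = 10%).

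**Outcome probabilities.** With q = 1 − p:

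- stopped with x = 0 or 1: C(10,x) p^x q^(10−x)
- completed with total s: W(s) p^s q^(20−s), where W(s) = Σ C(10,x) C(10,s−x) over x ≥ 2

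For example, W(2) = 45, W(3) = 45×10 + 120 = 570 and W(4) = 45×45 + 120×10 + 210 = 3,435. A fixed sample of 20 would have C(20,2) = 190 ways to reach a total of 2.

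**Stopping probability**, q^10 + 10pq^9: 73.6% at a true 10%, 37.6% at 20%, 14.9% at 30%, 4.6% at 40%.

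**Stage-wise interval.** Order the outcomes 0/10, 1/10, 2/20, 3/20 and so on, and invert each tail at 2.5%.

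| Result | Clopper-Pearson | Stage-wise exact | Upper-limit gap (points) |
|---|---|---|---|
| 2/20 | 1.2–31.7% | 2.5–44.6% | 12.9 |
| 3/20 | 3.2–37.9% | 4.1–45.1% | 7.2 |
| 4/20 | 5.7–43.7% | 6.3–47.0% | 3.3 |
| 5/20 | 8.7–49.1% | 9.0–50.4% | 1.3 |
| 6/20 | 11.9–54.3% | 12.1–54.7% | 0.4 |
| 7/20 | 15.4–59.2% | 15.5–59.3% | 0.1 |

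From 8/20 up, the limits agree within about 0.02 points.

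A check at 2/20: at p = 0.317 the probability of stopping is 0.683^10 + 10×0.317×0.683^9 = 0.125. The probability of 2/20 is 45×0.317²×0.683^18 = 0.005. The tail in this ordering is 0.13, not 0.025, so 31.7% is not its upper limit.

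**Coverage of Clopper-Pearson under the design**, by full enumeration:

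- It is 98.9%, 97.9%, 99.0%, 98.6% and 98.3% at true rates of 10%, 15%, 20%, 25% and 30%.
- It is below 95% only for true rates of about 44.6% to 45.7%.
- The minimum, at 44.6%, is 94.3%. The upper limits for 0/10, 1/10, 2/20, 3/20 and 4/20 all lie below 44.6%, and those outcomes have probabilities 0.0027 + 0.0219 + 0.0002 + 0.0022 + 0.0107, about 3.8%. The other tail adds 2.0%.

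The stage-wise interval holds at least 95% throughout.

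**Raw proportion.** Its expectation over all trials is 8.3%, 17.6% and 28.4% at true 10%, 20% and 30%, a bias of −1.7, −2.4 and −1.6 points.

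**How often low totals occur.** Among trials that pass, 2 to 4 of 20 makes up 86% at a true 10%, 67% at 15% and 46% at 20%. At a true 30% only 13.5% of all trials end there.

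**Overrun if accrual is not paused.** Rate × 8×7/30.44 months = 1.84 patients at 1 per month and 3.68 at 2 per month, so about 2 to 4 further starts.

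**The case against.** The strongest reply is that little depends on this. There is no success threshold, the futility decision uses raw counts, and the worst coverage loss is 0.7 points in a 20-patient pilot. That stands, and it sets the severity.

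A reader might infer that the interval fails just where an inactive or weakly active drug that passes would land. The coverage figures do not support that: at true rates of 10% to 30% both intervals cover 97.9% to 99.0%, and among passing trials Clopper-Pearson still covers 96.0% at 10%, 95.3% at 15% and 98.4% at 20%. What is misplaced is the upper limit at low totals.

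A reader might also call it incoherent that a pass ending at 2/20 has a lower ceiling (31.7%) than a stop at 1/10 (44.5%). Both are 10% observed, and more data narrows an interval. The order is anomalous only once stage-wise ordering is accepted.

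Replacing the raw rate with an adjusted estimate is tempting but is a trade-off. Among passing trials the raw rate is already high on average (16.6% at a true 10%, 23.9% at 20%), and the uniformly minimum-variance unbiased estimate (UMVUE) is higher still (23.2% and 27.7%). At 2/20 the median-unbiased estimate is 16.9% and the UMVUE is 20.0%, so leaving the choice open adds an analyst's decision.

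Finally, it cannot be said that 2 to 4 extra patients will be treated. The text that enrollment proceeds on a pass can be read as waiting; the text that it is aborted or discontinued can be read as ongoing. If 2 or 4 overrun patients were analysed after a futile stop, minimum Clopper-Pearson coverage would be 95.1% or 95.5%, so the shortfall itself depends on how they are handled.

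**Conclusion.** The point holds in a limited form. The planned interval is not exact under the binding rule: minimum coverage is 94.3%, upper-tail error is up to 3.8%, and upper limits are 3 to 13 points below the stage-wise limit at 2 to 4 of 20. From 6/20 up the difference is 0.4 points or less, and the raw rate's bias over all trials is 1.6 to 2.4 points downward at true rates of 10% to 30%. The documents do not support saying that the interim is ignored, since Section 15.1 mentions it; it is given no consequence for the interval. The accrual question is a gap to clarify.

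The interval and coverage figures assume exactly 10 + 10 patients and a rule that is followed. The overrun figure assumes no pause and the stated accrual rate. Whether low totals are likely depends on a true rate that the plan does not specify. The severity is low: an inexpensive improvement best made before data are seen.

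**What to change.** **Section 15.1, interval.** Report the raw count and proportion with the stage-wise-ordered exact 95% interval for the 10/20 design as the primary interval. Clopper-Pearson may be shown beside it. One adjusted point estimate may be added as a supplement if it is named in advance; it should not replace the raw proportion.

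**Sections 5.2 and 15.1, timing.** Allow the interim to be called once two of the first ten are confirmed successes (continue) or nine are confirmed failures (futile). The decision is the same and comes no later; all patients treated are still followed and counted. State what happens if the ninth failure is confirmed before the tenth patient starts, because the interval assumes a first stage of ten.

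**Sections 5.2 and 15.1, accrual.** State whether enrollment at the expansion dose pauses after patient 10 and how any overrun patients enter the estimate and interval.

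**Reconcile week-4 progression.** Section 5.6 schedules "MRI brain w/ and w/o contrast (after 4 weeks, after 8 weeks, every 8 weeks thereafter", so progression can be seen at week 4. Whether that is a final failure must be reconciled with the 8-week endpoint (Section 2), the provision for treatment beyond progression (Section 5.1) and the response definitions (Section 5.7). How much time an early call saves depends on how many failures show at week 4, which the documents do not give.

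**Cost.** A few sentences, a short program and somewhat wider intervals at low totals. The sample size and stopping threshold do not change.
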